Our research group has previously used this type of picture-based cue exposure procedure to successfully elicit craving in methamphetamine dependent individuals.^{69,70} Additionally, previous research by our group has shown that these pictures (subset of 10) elicit greater cocaine craving and subjective arousal in cocaine dependent individuals ($n = 27$; craving $\bar{x} = 5.9$ and arousal $\bar{x} = 10.1$) than in non-cocaine dependent controls ($n = 28$; craving $\bar{x} = .06$ and arousal $\bar{x} = 5.3$; both t 's > 3.6 , both p 's $< .001$). Furthermore, the mean craving and arousal reported by cocaine dependent individuals in response to the cocaine pictures was greater than the mean craving and arousal they reported in response to a set of neutral comparison pictures (craving $\bar{x} = 1.0$ and arousal $\bar{x} = 5.3$; both t 's > 4.5 , both p 's $< .0001$). Thus, we are confident these cocaine picture cues will serve as effective elicitors of craving and arousal in proposed study.

Procedure: At approximately 10:00 am, baseline subjective and physiologic outcome measures will be collected. Thirty minutes later, participants will receive the first sequence of CCE. Each sequence will consist of a 5-min video cocaine cue presentation followed immediately by in vivo cue presentation. Heart rate and SC data will be continuously collected during the first 50 sec of each cue type (video and in vivo). The CDMS Scale and BP will be obtained at the end of the in vivo cues. After the latter measures were obtained participants remained comfortably seated until the second, identical sequence of CCE commenced (approximately 5-10 min later). At the end of the CCE in the retrieval session, participants will receive their medication and complete all outcome measures. As indicated in figure 4, all dependent measures will be obtained immediately after CCE sequence and at 15 min. and 30 min. time points following termination of CCE. At the end of each retrieval session, research staff assisted the participant in removing the HR/SC leads and BP cuff. Participants will remain at the CTRC laboratory facility for an additional 60 min., at which time a blood draw will occur. The sample will

be used to determine plasma concentrations of the propranolol so that the association between propranolol level and treatment effects can be assessed; the timing of the blood draw was based on the observation that peak concentrations of propranolol are reached 90-min post administration.^{52,53} Also at this time, participants will be asked to complete a dual-item form that asks whether or not they thought they received propranolol or placebo and, for those who

Figure 4

thought they received propranolol, at what dose level (this data will be used to assess the effectiveness of the blind). Research staff will then escort the participant to a research dedicated hospital room where they will remain overnight. The second retrieval cue exposure session, occurring the following day at the same time, will be identical to the first in all respects, including the overnight stay at the Institute of Psychiatry (IOP). Prior to discharge from the IOP the next day, research staff will schedule a test/follow-up CCE session, remind the participant that it is important to maintain abstinence during the interim period between their inpatient stay and the test/follow-up session and also remind them that a significant portion of the compensation (i.e., \$75.00) available at the end of the test session will be contingent on a negative UDS. Our group has previously used a

modified version of the ‘fishbowl’ contingency management (CM)⁷¹ procedure to successfully achieve an 80% rate of UDS verified cocaine abstinence over a 3-day period. Since the ‘fishbowl’ CM procedure only offered a small probability of earning the level of monetary compensation we plan to guarantee in the proposed study, we expect the abstinence rates during the 2-4 day interim period to exceed 90%.

The goals of the first test/follow-up session will be to evaluate the acute effects of dual medicated (either 40 and 80 mg propranolol) retrieval CCE sessions on craving and cue reactivity and to assess the generalization for these effects to novel cocaine cues picture cues. This session will be scheduled to occur no earlier than two days after inpatient discharge and no more than 4 days (this 2-4 days window will permit flexibility in scheduling to accommodate weekends and participant scheduling needs). The details of the first test/follow-up CCE session are identical to those described above for the retrieval sessions with the following exceptions. First, no medications will be administered. Second, UDS/breathalyzer assessment and Timeline Follow-Back will be administered to determine if the participant had maintained abstinence during the interim period (all participants, regardless of abstinence status, will be administered the CCE). Third, approximately 45 min after the CCE (i.e., 15 min after the 30 min post-CCE assessment; see shaded area in procedure Figure 4), the picture-based novel CCE procedure described above will be administered. At the end of the picture-based CCE, participants will complete 2 additional sets of post-cue measurements. Study staff will then remove the HR and SC leads and the participant will remain seated comfortably for 10 min. Prior to discharge, participants will be reminded that they are entering the follow-up phase (2) and that they are encouraged to remain abstinent from cocaine use but that abstinence will not affect the compensation that they receive for attending their scheduled follow-up sessions. In the event that a participant experiences elevated craving at the end of a CCE session (i.e., report a post-session craving score $\geq 20\%$ above baseline), they will be asked to remain in the CTTC until their craving subsides. A member of the research staff will be available to discuss management of craving urges. Finally, study staff and the participant will schedule the three study visits that will occur over the ensuing week.

E. Phase 2 Follow-up Drug Use Assessments and Cocaine Cue Exposure (CCE) Sessions

Follow-up Assessment Sessions: The goals of the follow-up visits are to determine if (a) the effects of post-retrieval propranolol on craving and cue reactivity to both familiar and novel cocaine cues are sustained over the 6-week follow-up, and (b) the post-retrieval propranolol treatment(s) impact cocaine use (variously measured) during follow-up. There will be a total of 18 visits scheduled over 6 weeks, with three visits occurring per week. All follow-up visits will begin with a drug/alcohol assessment. Briefly, participants will meet research staff at MUSC’s CTTC at approximately 9:00 a.m. on the pre-arranged day. At this time, a UDS and breathalyzer measurement will be obtained; cocaine, alcohol and other drug use status will be recorded. Next, research staff will perform a Timeline Follow-Back in order to ascertain the level of drug/alcohol use during the days since their last study visit. On follow-up visits that occur at the end of weeks 1, 3 and 6, participants will undergo a CCE session that is identical to the test session described above (test/follow-up CCE will follow drug/alcohol assessment). On these occasions, the cue exposures procedures will commence at approximately 10:30 a.m. to ensure that all study CCE sessions are being performed at approximately the same time of day (thereby serving to minimize the impact of circadian variation in sex and stress hormone levels on outcomes). Following CCE administration, the participant and staff will confirm the next appointment times and the appropriate level of compensation provided (see compensation plan below). At the end of each week, all appointments for the ensuing week will be scheduled. At the conclusion of the 6-week follow-up period, participants will be asked if they would like referrals for treatment

F. CCE Session Instruments and Related Measures

Self Report Measures

State-Trait Anxiety Inventory (STAI): The STAI is a 20-item self-report scale⁷² employing a Likert-scale format with four responses per item (1-4). Ten of the STAI items measure feelings of stress and anxiety, while the remaining ten items measure feelings of relaxation.

Cocaine Selective Severity Assessment (CSSA): The CSSA is an 18-item interview-based measure⁷³ of cocaine withdrawal symptom severity (e.g., lethargy, sleep disturbances, lethargy). It will be used to assess the association between withdrawal symptom severity and treatment response.

Beck Depression Inventory (BDI): The BDI is a 21-item scale⁷⁴ that is a gold standard for the self-report assessment of depressed mood. The BDI will be administered at the screening visit and last study visit.

Adverse Events Form (AEF): We have used this instrument in many of our past to assess medication side effects/adverse events. The AEF will be administered at all study visits (i.e., end of inpatient stay and all test/follow-up visits).

Craving/Distress/Mood States (CDMS) Scale: This scale is a modified version of the Within Session Rating Scale^{75,76} and was used in the R21 and in several past^{77,78} and ongoing cue-reactivity protocols by our group. This self-report assessment contains thirteen, 100 mm visual analogue scales, with each being anchored by the adjectival modifiers “not at all” (left side of scale) and “extremely” (right side of the scale). The craving item asks the participant to rate the desire to use cocaine “right now”. The remaining items assess other drug-related subjective states (withdrawal, anxiety, frustration, anger, depressed mood, etc.). Figure 4 shows the timing of administration of this scale within the CCE sessions.

Cocaine Craving Questionnaire- Brief (CCQ): The CCQ is a 10-item scale used to assess the participant's feelings and thoughts about using cocaine at that moment in time. This will be assessed at the end of CCE sessions.

Physiological Measures

Heart rate (HR), blood pressure (BP) and skin conductance (SC) were measured as indices of physiological arousal during each CCE session. Heart rate was collected via two electrodes, with one affixed to the right shoulder and the other on the bottom left side of the participant's ribcage. Blood pressure was measured using an intermittently inflatable cuff. Because this measure cannot be obtained unobtrusively, it will be taken at the same time as the CDMS is obtained (see figure 4 above). Skin conductance was recorded using Ag/AgCl electrodes attached to the skin over the metacarpal bone of the fifth digit, non-dominant hand. Since physiological arousal/reactivity was likely to be greatest in the earliest portions of a CCE sequence, HR and SC data will be continuously collected during the initial 50-second epoch of each video and in-vivo cue presentation and during the first 50-sec of the novel picture-based CCE (they also are collected at baseline and at 15-min and 30-min follow-up time points; see figure 4). The HR and SC signals will be amplified using the ECG 100c and GSR 100c Modules of the Biopac MP100 data acquisition system; the Biopac system will be interfaced with an Apple (MacBook Pro) laptop for data storage and subsequent reduction. While the HR, BP and SC measures obtained in the second medicated retrieval session may be impacted by the medication (not in the first retrieval session since the medication is administered after the CCE), it should be noted that these responses are not relevant to the evaluation of any hypothesis. Nonetheless, these responses will likely provide some measure/indication of the effects of the first medicated retrieval.

G. Participant Compensation

Participants will receive \$50.00 for completing the initial assessment. There will be a \$10.00 incentive if the participant shows up on their originally scheduled date and within 15 minutes of their scheduled time. The participant will be compensated \$25.00 for the urine drug screen the day before admission to the IOP if they produce a negative urine drug screen. There will be \$200.00 given to the participant for completing the inpatient portion of the study (\$100.00 for each over night stay at the CTRC, including completion the retrieval CCE session). Compensation will only be provided in full when a participant completes the entirety of the overnight stays. Participants will not be able to collect a partial payment for completing only a portion of the overnight stays. Compensation for attending the test/follow-up session (2-4 days following discharge from the CTRC) will have three components; to encourage attending this session, \$50.00 compensation will be provided; to increase the likelihood that cocaine abstinence since the time of their CTRC discharge is achieved, an additional \$75.00 incentive will be available if participants provide a cocaine negative urine drug screen (UDS). Lastly, an additional incentive of \$25 dollars will be contingent on their attending the test session on the scheduled day and time. Thus, the maximum compensation for Phase 1 participation is \$435.00 (\$60.00+\$25.00+\$200.00+\$150.00). Compensation for these Phase 1 visits (the screening and these first three visits) will be provided at the end of the first test/follow-up session (visit 3). Compensation will only be provided in full for completion of all these sessions excepting in cases of medical withdrawal and not cases of violating protocol. Phase 2 (follow-up) of the proposed study will be 6-weeks in duration and will involve 3 visits to MUSC each week for a total of 18 visits. For each of the 15 visits that they are scheduled to provide a urine drug screen (UDS) and undergo a Timeline Follow-Back assessment (TLFB), they will be compensated \$25.00. For each of the 3 visits they are scheduled to provide a UDS, TLFB and undergo CCE session, they will be compensated \$75.00. Additionally, participants will receive a bonus payment of \$50.00 at the end of each follow-up week if they have attended all 3 weekly visits as scheduled. Accordingly, the maximum compensation attainable in Phase 2 will be \$900.00 [(15 x \$25 = \$375.00)+(3 x \$75.00 = \$225.00)+(6 x 50 = \$300.00)]. The total maximum compensation for both phases of the study will be \$1,335.00. If it is found that a

participant has provided false information regarding his or her identity, the PI has the right to withhold payment for their current visit and drop the participant from the study.

Respondent-Driven Sampling (RDS) will be used to enhance recruitment of the sample. The RDS sampling methodology is based on recruiting the eligible friends and acquaintances of each participant so that the sample “snowballs.” Each eligible participant who is enrolled into the study, and agrees to take part in this recruitment assistance, will be given business cards and/or flyers to pass on to other potential participants. A referral will be instructed to call the site offices for screening and, if eligible, an appointment for further evaluation. The referral and the participant who made the referral must acknowledge the other party. If a referral completes the screening, overnight visits, and first follow-up visit, or phase 1 of the study, then the participant who made the referral will be compensated \$20. Participant will receive cash payment at next visit or in person after the successful referral.

While this level of compensation may raise concerns that money earned from research participation could be used to purchase drugs or could be perceived as coercive, evidence from our prior studies (including the R21) as well as research by others⁷⁹ suggests that these concerns are not warranted. The details of these study findings are discussed in the Protection of Human Subjects section of this application.

H. Data Management and Data Analytic Plan

Research staff will perform data entry for self-report and ratings measure (under the supervision [name], Co-I). Random data entry checks will both assess and enhance data integrity. Heart rate and skin conductance data will be acquired via specialized software and hardware (Biopac Systems, Inc.) interfaced with an Apple MacBook Pro computer. Standardized file formats will facilitate the rapid determination of summary values to be used for analysis purposes.

Outcome Measures

The main cue reactivity outcome measures for the Phase 1 are subjective craving and physiological reactivity. Summary mean and peak values for craving (and related subjective measures) will be computed for all CCE sessions administered over the course of the study (i.e., all retrieval and test/follow-up sessions). Outcomes for the physiological measures (heart rate, skin conductance and blood pressure) will be computed in a similar fashion. However, data reduction on the HR and SC measures will precede computation of the summary values. The main cocaine use outcomes in Phase 2 will be (1) latency (days) to first use, (2) number of cocaine using days during follow-up, (3) dollar amount of cocaine used during follow-up, and (4) proportion of positive vs. negative UDS. Summary values on outcome measures obtained during the first retrieval CCE session (i.e., before any medication is administered) will serve as baseline (cue-elicited) outcomes and will be used as covariates in the data analytic plan described below.

Data Analysis Plan

Baseline demographic and clinical measures will be compared across treatment groups using standard statistical methods. Categorical demographic/clinical variables will be analyzed using Pearson chi square tests of independence while continuous demographic/clinical variables will be compared using one-way ANOVA procedures.

Phase 1. The first component of hypothesis 1 is that participants receiving propranolol (40 mg and 80 mg) compared to placebo treated controls, will evidence significantly lower cocaine craving and physiological reactivity (HR, SBP, DBP) during the first test/follow-up CCE session. To test this a priori hypothesis, a generalized linear mixed effects model will be developed using model-based estimates to construct group level contrasts (40PP & 80PP combined vs. PBO). A separate contrast will be developed to test the second component of hypothesis 1 that relative to the group 40PP, the group 80PP will evidence lower levels of craving and cue reactivity. Since the expected response pattern characterized in both components of hypothesis 1 is expected to occur to the novel picture cues presented at the end of the test session, a similar analytic plan will be adopted to evaluate the secondary hypothesis.

Phase 2. The hypothesis (2) that propranolol treated individuals (40PP and 80PP combined), as compared to placebo treated controls, will evidence less cocaine use during the 6-week follow up will be assessed across a limited set of outcomes. Analysis of variance models will be used to assess the continuous outcomes such as the mean number of days reported using and dollar amount spent on cocaine during the follow up. The overall proportion of participants relapsing to cocaine usage will be assessed using logistic regression models to test if differences exist between the propranolol and placebo treated participants at the end of the follow up period. To test the latency to return to cocaine use, Cox proportional hazards regression models will be used to assess both time to first positive UDS/self reported cocaine use as well as time to second positive UDS/self reported use.

In order to fully utilize the longitudinal data, additional analysis will test the pattern of positive UDS data over the entire course of the follow up (measured 3 x weekly for 6 weeks). These models will be developed through the use of generalized linear mixed effects models.^{80,81} To test the hypothesis (3) that participants treated with propranolol (40PP and 80PP) vs. placebo will evidence less craving and cue reactivity to both familiar and novel cocaine cues presented during test/follow-up CCE sessions, linear mixed effects models will be developed. The models will explore the effects of treatment, time, cocaine use status, and the interactions of the factors on the craving and physiologic responses to cocaine cues presented during the week 1, 3 and 6 test/follow up CCE sessions.

Secondary Analysis. There are a number of secondary analyses of interest. First, it is possible that propranolol will begin affecting craving and cue reactivity as early as the second retrieval session. Therefore, we will use a linear mixed effects model to identify between group differences that develop in the second retrieval session. Second, it is expected that propranolol's ability to disrupt reconsolidation will be related to its bioavailability, which we will index using the plasma sample obtained approximately 90 min after each medication administration. We plan to use regression analyses to assess whether plasma concentrations of propranolol predict variation in the outcome measures (e.g., craving, cue reactivity and cocaine use) obtained across the test/follow-up CCE. Third, we plan to evaluate whether treatment impacts ambient or background craving and cue reactivity^{82,83} (i.e., non-cue-elicited outcomes obtained a half hour before each test/follow-up CCE session) using linear mixed effects models. The models will also test the effects of time and cocaine use status. Fourth, since there is some evidence of gender differences in propranolol metabolism^{84,85} and adrenergic functioning in emotional memory^{86,87}, we will examine associations between gender and treatment outcome. Fifth, we plan to evaluate the effectiveness of the participant blind. Specifically, responses obtained from the participants about which medication group (propranolol dose vs. placebo) they thought they were in will be contrasted with the medication condition to which they were randomized and analyzed via a Pearson chi square test of independence.

Missing Data. Since data for all medicated retrieval CCE sessions in Phase 1 will be collected while the participants are residing at the CTTC, missing data or study dropouts are not anticipated. Inevitably, over the 6-week follow up period, missing cue reactivity and cocaine use data will occur. The missing observations might be 'unit missing', which occurs when a participant does not present at one or more of the time points. The unit missing will be treated as though they are missing (completely) at random. Methods such as multiple imputations⁸⁸ using PROC MI and PROC MIANALYZE will be considered. With respect to the UDS data we will also perform a sensitivity analysis by treating any missing UDS as positive and reanalyzing the data.

I. Alternative Design Considerations and Potential Study Limitations

1. Propranolol Dosing: We considered three dosage increases for use in the proposed study; 60 mg, 80 mg and 120 mg. The decision to employ 80 mg dosage was based on the following rationale. An 80 mg dosage represents a doubling of the 40 mg used in the R21, which is conceptually congruent with the doubling of the medicated retrievals from one in the R21. From a pharmacokinetic perspective, it is known that the bioavailability of propranolol is rather modest (Approximately 25%) and variable⁵⁷ so it was important that the dosage increase be sufficiently large to ensure an appreciable increase in plasma concentration and therefore, increased availability in the brain. Accordingly, it seemed likely that the 80 mg dosage would, on balance, achieve a substantial increase in central availability without sizably increasing risk of sinus bradycardia or a hypotensive episode. Furthermore, there have been several human laboratory^{89,90} and clinical studies⁹¹ on single or dual administrations of 80 mg or more of propranolol with no reported adverse effects. These observations, together with the fact that participants will remain at the CTTC for both medication administrations, increased our confidence about the safety of using 80 mg while at the same time achieving a biologically significant increase in propranolol plasma concentrations.

2. Number of Medicated retrieval sessions. While it is reasonable to assume that multiple medicated retrieval CCE sessions may cumulatively interfere with memory reconsolidation, there are no human laboratory or clinical studies to guide decision-making regarding incremental utility of additional medicated retrievals. As noted above, there are two infrahuman studies^{42,59} showing that 10 or more medicated retrievals achieve large DoR effects. However, these studies don't address the possibility that substantially fewer medicated retrievals may be all that is needed to achieve a significant augmentation of DoR. Moreover, high numbers of medicated retrieval sessions detract from the practical value and feasibility of DoR-based treatment. In the absence of any definitive empirical support regarding this decision, we have elected to double the number medicated retrievals employed in the R21. This decision represents an attempt to balance the goal of DoR augmentation with the increase in participant burden (i.e., more over night stays at CTTC), design complexity and difficulty interpreting the findings

(i.e., at what point does the amount of stimulus exposure require a transition from a reconsolidation to an extinction level of analysis⁴⁵).

3. Non-treatment seeking sample. As in the case of the R21, non-treatment seeking cocaine dependent participants will be recruited for this study. We have elected to use non-treatment seekers because we have evidence from our previous laboratory studies⁹² and from the R21 that non-treatment seekers essentially behave as though they are seeking treatment. That is, they often exhibit abstinence rates and reductions in cocaine use that are similar to levels observed in formal treatment outcome studies.⁹³⁻⁹⁵ For example, 60-65% of the R21 sample reported no cocaine use at 1-week follow-up and their dollar amount of cocaine use decreased 85% from pre-study levels. Since main goal of the follow-up is to track individuals who have substantially reduced their cocaine use as they gradually return to substance use over a 6-week period and assess whether or not DoR retards the return to cocaine use, we believe that employing non-treatment seekers will permit attainment of this goal. Additionally, because the goal of the proposed study is to document the treatment potential of DoR, recruitment of treatment seekers seems premature.

J. Future Directions

Positive findings from the proposed study could lead to a phase III RCT in which a DoR treatment element is added to multi-component intervention to assess its incremental treatment utility. Because a DoR-based treatment component would be both brief and easy to integrate with other therapies, it would be relatively simple to evaluate it in the context of extant and new behavioral and pharmacotherapy combinations^{96,97} as well as with the emerging cocaine vaccine.⁹⁸ Furthermore, since a DoR-based treatment targets the learning/memory processes underlying all forms of addictive behavior rather than a specific neurotransmitter system (i.e., GABA), it may have broader clinical utility and therefore be useful in treating addiction to a wide range of substances (e.g., cigarette smokers, opiate addicts, marijuana addicted young adults, etc.).

K. Operational Plan and Research Timetable

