Phase 1. In the proposed study, random effects ANOVA procedures will be used to assess differences among three treatment arms (placebo = PBO, 40 mg propranolol = 40PP, and 80 mg propranolol = 80PP). The over arching goal of the sample size estimation was to ensure the study will be sufficiently powered to adequately detect effect sizes that are both relevant to the study hypotheses and clinically meaningful. We restricted the Phase 1 estimation to the key outcome measure of subjective craving, as it has the largest standard deviation of all outcome measures. Drawing from the R21 results presented above, the subjective craving response following treatment with 40 mg of propranolol decreased 24.2 ± 24.7 points (mean \pm SD, change on a 100 point scale) while the group treated with placebo was found to decrease 8.8 ± 19.9 points. This yields a Cohen's d of $(15.4/22.3) = 0.69$. In the proposed study, we want to be able to detect craving differences, should they exist, between the PBO and 40PP group and between the 40PP and 80PP group. Additionally, we will make the conservative assumptions that (a) the difference between the PBO and 40PP groups will be 10% smaller than observed in the R21; $d = 13.9/22.3 = .62$, and (b) the difference between the 40PP and 80PP groups will be substantially (30%) smaller than the difference observed in the R21; $d = 11.6/22.3 = .52$. Accordingly, assuming

a pooled SD of 22.3, an $\alpha = .05$, and 60 participants randomized to each of three treatment groups, we will have 86% power to detect a $d = .62$ between the PBO and 40PP groups (i.e., craving difference of 13.9 units) and 80% power to detect a $d = .52$ between the 40PP and 80PP groups (i.e., craving difference of 11.6 units).

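### Phase 1 power paragraph: the 40PP vs 80PP difference labelled 30% smaller is about 25% smaller, and the 86% power for d = .62 should be about 92% on the stated inputs

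*Combined protocol and SAP*

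**What the plan says.** The Phase 1 paragraph of Sample Size Estimation (section 3.B) starts from the R21 craving results. The 40 mg group "decreased 24.2 ± 24.7 points", while "the group treated with placebo was found to decrease 8.8 ± 19.9 points". The difference is 15.4 points, which the plan divides by an SD of 22.3 to give d = 0.69.

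The plan then shrinks this difference in two ways and calls both assumptions conservative:

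- PBO vs 40PP: the difference "will be 10% smaller than observed in the R21; $d = 13.9/22.3 = .62".
- 40PP vs 80PP: the difference is "substantially (30%) smaller than the difference observed in the R21; $d = 11.6/22.3 = .52".

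Both power figures rest on one set of inputs: SD 22.3, a single alpha of .05 with no sidedness given, and "60 participants randomized to each of three treatment groups". On these the plan states that "we will have 86% power to detect a $d = .62$ between the PBO and 40PP groups" and that there is "80% power to detect a $d = .52$ between the 40PP and 80PP groups (i.e., craving difference of 11.6 units").

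The Data Analysis Plan (section 3.H, Phase 1) makes the dose comparison one of the two contrasts for hypothesis 1: "A separate contrast will be developed to test the second component of hypothesis 1 that relative to the group 40PP, the group 80PP" will show less craving and cue reactivity. The other contrast is the two propranolol arms combined against placebo.

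**The concern.** Two figures in the paragraph do not follow from what surrounds them.

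First, both reductions are taken from the same 15.4-point reference. The 10% reduction is applied correctly, but the 30% reduction does not lead to 11.6 points. A reader who relies on the percentage will think the study has 80% power under a more cautious assumption than the one actually used. The dose contrast is a named hypothesis, and this paragraph is the stated justification of the Phase 1 sample size.

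Second, the two effect sizes share one n, one SD and one alpha, so their power figures are tied together. If d = .52 has 80% power, d = .62 must have clearly more than 86%. One of the two figures must therefore rest on inputs that the paragraph does not state.

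**Working it through.** **Inputs, all from the Phase 1 paragraph:** R21 changes of 24.2 (SD 24.7) and 8.8 (SD 19.9) points; SD 22.3; alpha .05; 60 per arm. Two-sided testing is an assumption.

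**Step 1: percentages**

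- R21 difference: 24.2 − 8.8 = 15.4 points; 15.4/22.3 = 0.69, as stated.
- 10% smaller: 15.4 × 0.90 = 13.86, printed as 13.9. This agrees.
- 30% smaller: 15.4 × 0.70 = 10.78 points, and 10.78/22.3 = .48. The plan prints 11.6 and .52.
- Reduction implied by 11.6: 1 − 11.6/15.4 = 0.247, or 24.7%. A 25% reduction gives 15.4 × 0.75 = 11.55.

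Rounding cannot close a gap of 11.6 − 10.78 = 0.82 points. Taking the reduction from 13.9 instead does not help, because 11.6 is 16.5% below 13.9. This step needs no assumption about the test.

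**Step 2: power on the stated inputs**

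For a two-sample t-test with n per arm, the noncentrality is d × √(n/2), here d × √30 = d × 5.477, with 118 degrees of freedom. The normal approximation is Φ(d × 5.477 − 1.960).

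| Difference | d | Noncentrality | Normal approx. | Noncentral t | Plan states |
|---|---|---|---|---|---|
| 11.6 | .520 | 2.849 | 81.3% | 80.7% | 80% |
| 13.9 | .623 | 3.414 | 92.7% | 92.3% | 86% |
| 10.78 | .483 | 2.648 | 75.4% | 74.7% | – |

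With d rounded to .62 the noncentral t gives 92.0%. The stated 80% reproduces and the 86% does not. At 60 per arm, 86% power corresponds to d = .56 (12.5 points, 19.0% below 15.4), and 80% power to 11.5 points (25.3% below 15.4).

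**Step 3: can other inputs explain both figures?**

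| Variant | 13.9 points | 11.6 points |
|---|---|---|
| One-sided .05 | 96.0% | 88.3% |
| 48 per arm (the Phase 2 follow-up number) | 85.6% | 71.3% |
| Two-sided alpha .025 for both | 87.2% | 71.8% |
| Tukey pairwise, three arms | 85.2% | 68.6% |
| SD 24.7 | 86.4% | 72.3% |
| SD 22.5 | 91.9% | 80.0% |
| Three-arm error df (177) | 92.4% | 80.9% |

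The variants that come near 86% all miss 80%. The choice of pooled SD does not explain the gap either: 22.3 is the simple mean (24.7 + 19.9)/2, while the root mean square is 22.43 and the version weighted by the R21 arm sizes (26 and 24) is 22.53. Either lowers power by less than one point.

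A search over 40 to 80 per arm and alpha from .01 to .10, one- and two-sided, found no single setting that gives both figures. Where d = .52 has about 80% power, d = .62 has 89.8% to 93.0%. Where d = .62 has about 86%, d = .52 has 68.6% to 74.4%.

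**The case against.** Five points can be made for the plan.

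- **Split alpha.** If alpha .05 is family-wise and split in steps, with .025 for the larger effect and .05 for the smaller, power is 86.8% for d = .62 and 80.6% for d = .52. These truncate to the plan's figures. It is a possible origin, but the plan describes no such procedure, the paragraph gives one alpha for both comparisons, and 86.8% would normally be rounded to 87%. What stands is that the sponsor should be free to state a different basis rather than only to correct the number.
- **The power claim for the dose contrast is consistent.** It is tied to d = .52 and 11.6 points, not to the percentage. This stands, and it makes a mislabelled percentage the simpler reading: 11.6 and .52 each appear twice and agree with the 80%.
- **Enrolment rose to 200, about 67 per arm.** At 67 analysed per arm, 10.78 points has 79.3% power and 11.6 points has 84.8%. However, the Participants and Recruitment sections say the increase is meant to secure enough completers, so 67 analysed is an upper bound. A fair range for a true 30% reduction is about 75% to 79%.
- **The planned model adjusts for first-retrieval values.** This could raise power, but no correlation is given. The figures here, like the plan's, are for unadjusted change scores.
- **The 86% is on the safe side.** It understates power, and it concerns a pairwise comparison that section 3.H does not name as a separate contrast. This stands.

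**Conclusion.** Both parts hold, and the point is minor. The 30% label is wrong for the number used: 11.6 points is 24.7% below 15.4, and a real 30% reduction is 10.8 points (d = .48), with 74.7% power at 60 per arm instead of 80%. That arithmetic on the label rests on the plan's figures alone. The 86% for d = .62 is about 6 points too low on the stated inputs, which give 92.0% to 92.3%.

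The power figures assume a two-sided test, an unadjusted alpha of .05 and all 60 per arm analysed. Two-sided is the natural reading because it reproduces the stated 80%, whereas one-sided matches neither figure.

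The first discrepancy makes the calculation look more cautious than it is. The second errs the other way and does no harm to the sample size.

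**What to change.** Reword the one paragraph:

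1. Make the percentage and the number agree. The simpler way is to call the 40PP vs 80PP assumption about 25% smaller and keep 11.6 points, d = .52 and 80% power. If 30% was intended, give 10.8 points, d = .48 and about 75% power at 60 per arm.
2. Replace 86% with about 92%, or state the different n or alpha on which the 86% rests.
3. State next to alpha whether the test is one- or two-sided, and whether alpha applies to each comparison or to both together.

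The cost is the wording of one paragraph. Enrolment, tests and outcomes stay as they are.
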